**Progressive Disease (PD) – ANY of the following:**

- Greater than or equal to 25% increase in the sum of the products of perpendicular diameters of enhancing lesions compared to the smallest tumor measurement obtained either at baseline (if no decrease) or best response, on stable or increasing dose of corticosteroids\*.
- Significant increase in T2/FLAIR non-enhancing lesion on stable or increasing dose of corticosteroids compared with baseline scan or best response following initiation of therapy\*, not due to co-morbid events (eg, radiation therapy, demyelination, ischemic injury, infection, seizures, post-operative changes, or other treatment effects).

- Any new lesion.
- Clinical deterioration not attributable to other causes apart from the tumor (eg, seizures, medication side effects, complications of therapy, cerebrovascular events, infection, etc.) or changes in corticosteroid dose.
- Failure to return for evaluation due to death or deteriorating condition.
- Clear progression of non-measurable disease.

\*Stable doses of corticosteroids includes patients not on corticosteroids.

**Stable Disease (SD):**

- Does not qualify for CR, PR, or PD.
- Stable non-enhancing (T2/FLAIR) lesions on same or lower dose of corticosteroids compared with baseline scan. In the event that the corticosteroid dose has been increased, the last scan considered to show SD will be the scan obtained when the corticosteroid dose was equivalent to the baseline dose.
- Stable clinically.

**Table 6. Overall Response Criteria**

|                         | CR   | PR   | SD    | PD |
|-------------------------|-------------|-------------|--------------|-----------------------|
| T1-Gd                   | None        | ≥50%↓       | <25%↑- <50%↓ | ≥25%↑*                |
| T2/FLAIR                | Stable or ↓ | Stable or ↓ | Stable or ↓  | ↑*                    |
| New Lesion              | None        | None        | None         | Present*              |
| Corticosteroids         | None        | Stable or ↓ | Stable or ↓  | NA                    |
| Clinical Status         | Stable or ↑ | Stable or ↑ | Stable or ↑  | ↓*                    |
| Requirement of response | All         | All         | All          | Any*                  |

1. Progression occurs when any of the criteria with \* are present; NA: increase in corticosteroid dose alone will not be taken into account in determining progression in the absence of persistent clinical deterioration

CR=complete response; PR=partial response; SD=stable disease; PD=progressive disease; ↓=decrease; ↑=increase

#### 7.4.1. F-18-FLT PET

For locations that are able to perform the tumor evaluation by F-18-FLT-PET, assessment will be performed in all patients assigned to receive doses of 500 mg QD or 500 mg BID or higher. Assessment will be performed at screening after all other eligibility criteria has been confirmed and again at Week 9 and Week 25 (Zhao et al, 2014; Corroyer-Dulmont et al, 2013). F-18-FLT-PET should be performed at the end of treatment visit if the patient discontinues the study prior to Week 9 or between Weeks 9 and 25 if more than 4 weeks have passed since the last evaluation.

CCI [REDACTED]

CCI [REDACTED]

CCI [REDACTED]

CCI [REDACTED]

CCI [Redacted]

CCI [Redacted]

CCI [Redacted]

CCI [Redacted]

CCI [Redacted]

CCI [Redacted]

I [Redacted]

I [Redacted]

[Redacted]

CCI [Redacted]

CCI [Redacted]

CCI [Redacted]

CCI [REDACTED]

CCI [REDACTED]

[REDACTED]

CCI [REDACTED]

CCI [REDACTED]

CCI [REDACTED]

CCI [REDACTED]

| [REDACTED]

| [REDACTED]

| [REDACTED]

| [REDACTED]

[REDACTED]

[REDACTED]

[REDACTED]

## **8. ADVERSE EVENT REPORTING**

### **8.1. Adverse Events**

All observed or volunteered AEs regardless of treatment group or suspected causal relationship to the investigational product(s) will be reported as described in the following sections.

For all AEs, the investigator must pursue and obtain information adequate both to determine the outcome of the AE and to assess whether it meets the criteria for classification as an SAE requiring immediate notification to Pfizer or its designated representative. For all AEs, sufficient information should be obtained by the investigator to determine the causality of the AE. The investigator is required to assess causality. Follow-up by the investigator may be required until the event or its sequelae resolve or stabilize at a level acceptable to the investigator, and Pfizer concurs with that assessment.

As part of ongoing safety reviews conducted by the sponsor, any non-serious AE that is determined by the sponsor to be serious will be reported by the sponsor as an SAE. To assist in the determination of case seriousness, further information may be requested from the investigator to provide clarity and understanding of the event in the context of the clinical study.

### **8.2. Reporting Period**

For SAEs, the active reporting period to Pfizer or its designated representative begins from the time that the patient provides informed consent, which is obtained prior to the patient's participation in the study, ie, prior to undergoing any study-related procedure and/or receiving investigational product, through and including 28 calendar days after the last administration of the investigational product. SAEs occurring to a patient after the active reporting period has ended should be reported to the sponsor if the investigator becomes aware of them; at a minimum, all SAEs that the investigator believes have at least a reasonable possibility of being related to investigational product are to be reported to the sponsor.

AEs (serious and non-serious) should be recorded on the CRF from the time the patient has taken at least 1 dose of investigational product through the patient's last visit.

- If a patient begins a new anticancer therapy, the AE reporting period for non-serious AEs ends at the time the new treatment is started. Death must be reported if it occurs during the SAE reporting period after the last dose of investigational product, irrespective of any intervening treatment.

### **8.3. Definition of an Adverse Event**

An AE is any untoward medical occurrence in a clinical investigation patient administered a product or medical device; the event need not necessarily have a causal relationship with the treatment or usage. Examples of AEs include but are not limited to:

- Abnormal test findings;

- Clinically significant symptoms and signs;
- Changes in physical examination findings;
- Hypersensitivity;
- Drug abuse;
- Drug dependency.

Additionally, they may include the signs or symptoms resulting from:

- Drug overdose;
- Drug withdrawal;
- Drug misuse;
- Drug interactions;
- Extravasations;
- Exposure during pregnancy (EDP);
- Exposure via breastfeeding;
- Medication error;
- Occupational exposure;
- Worsening of signs and symptoms of the malignancy under study should be reported as AEs in the appropriate section of the CRF. Disease progression assessed by measurement of malignant lesions on radiographs or other methods should not be reported as AEs.

#### **8.4. Medication Errors**

Medication errors may result, in this study, from the administration or consumption of the wrong product, by the wrong patient, at the wrong time, or at the wrong dosage strength. Such medication errors occurring to a study participant are to be captured on the medication error CRF, which is a specific version of the AE page, and on the SAE form when appropriate. In the event of medication dosing error, the sponsor should be notified immediately.

Medication errors are reportable irrespective of the presence of an associated AE/SAE, including:

- Medication errors involving patient exposure to the investigational product;

- Potential medication errors or uses outside of what is foreseen in the protocol that do or do not involve the participating patient.

Whether or not the medication error is accompanied by an AE, as determined by the investigator, the medication error is captured on the medication error version of the AE page and, if applicable, any associated AEs are captured on an AE CRF page.

### **8.5. Abnormal Test Findings**

The criteria for determining whether an abnormal objective test finding should be reported as an AE are as follows:

- Test result is associated with accompanying symptoms; and/or
- Test result requires additional diagnostic testing or medical/surgical intervention; and/or
- Test result leads to a change in study dosing or discontinuation from the study, significant additional concomitant drug treatment, or other therapy; and/or
- Test result is considered to be an AE by the investigator or sponsor.

Merely repeating an abnormal test, in the absence of any of the above conditions does not constitute an AE. Any abnormal test result that is determined to be an error does not require reporting as an AE.

### **8.6. Serious Adverse Events**

A serious adverse event is any untoward medical occurrence at any dose that:

- Results in death;
- Is life-threatening (immediate risk of death);
- Requires inpatient hospitalization or prolongation of existing hospitalization;
- Results in persistent or significant disability/incapacity (substantial disruption of the ability to conduct normal life functions);
- Results in congenital anomaly/birth defect;
- Progression of the malignancy under study (including signs and symptoms of progression) should not be reported as an SAE unless the outcome is fatal within the safety reporting period. Hospitalization due to signs and symptoms of disease progression should not be reported as an SAE. If the malignancy has a fatal outcome during the study or within the safety reporting period, then the event leading to death must be recorded as an AE and as an SAE with CTCAE) grade 5 (see the section on [Severity Assessment](#)).

Medical and scientific judgment is exercised in determining whether an event is an important medical event. An important medical event may not be immediately life-threatening and/or result in death or hospitalization. However, if it is determined that the event may jeopardize the patient or may require intervention to prevent one of the other AE outcomes, the important medical event should be reported as serious.

Examples of such events are intensive treatment in an emergency room or at home for allergic bronchospasm; blood dyscrasias or convulsions that do not result in hospitalization; or development of drug dependency or drug abuse.

### **8.6.1. Protocol-Specified Serious Adverse Events**

There are no protocol-specified SAEs in this study. All SAEs will be reported by the investigator as described in previous sections and will be handled as SAEs in the safety database (see the section on [Serious Adverse Event Reporting Requirements](#)).

### **8.6.2. Potential Cases of Drug-Induced Liver Injury**

Abnormal values in aspartate aminotransferase (AST) and/or alanine aminotransferase (ALT) levels concurrent with abnormal elevations in total bilirubin level that meet the criteria outlined below in the absence of other causes of liver injury are considered potential cases of drug-induced liver injury (potential Hy's law cases) and should always be considered important medical events.

The threshold of laboratory abnormalities for a potential case of drug-induced liver injury depends on the patient's individual baseline values and underlying conditions. Patients who present with the following laboratory abnormalities should be evaluated further to definitively determine the etiology of the abnormal laboratory values:

- Patients with AST or ALT and total bilirubin baseline values within the normal range who subsequently present with AST or ALT values  $\geq 3$  times the upper limit of normal ( $\times$  ULN) concurrent with a total bilirubin value  $\geq 2 \times$  ULN with no evidence of hemolysis and an alkaline phosphatase value  $\leq 2 \times$  ULN or not available;
- For patients with preexisting ALT **OR** AST **OR** total bilirubin values above the ULN, the following threshold values should be used in the definition mentioned above:
- For patients with preexisting AST or ALT baseline values above the normal range, AST or ALT value  $\geq 2$  times the baseline values and  $\geq 3 \times$  ULN, or  $\geq 8 \times$  ULN (whichever is smaller);

Concurrent with

- For patients with pre-existing values of total bilirubin above the normal range: Total bilirubin level increased from baseline by an amount of at least  $1 \times$  ULN **or** if the value reaches  $\geq 3 \times$  ULN (whichever is smaller).

The patient should return to the investigational site and be evaluated as soon as possible, preferably within 48 hours from awareness of the abnormal results. This evaluation should include laboratory tests, detailed history, and physical assessment. The possibility of hepatic neoplasia (primary or secondary) should be considered. In addition to repeating measurements of AST and ALT, laboratory tests should include albumin, creatine kinase, total bilirubin, direct and indirect bilirubin, gamma-glutamyl transferase, prothrombin time (PT)/international normalized ratio (INR), and alkaline phosphatase. A detailed history, including relevant information, such as review of ethanol, acetaminophen, recreational drug, and supplement consumption, family history, occupational exposure, sexual history, travel history, history of contact with a jaundiced person, surgery, blood transfusion, history of liver or allergic disease, and work exposure, should be collected. Further testing for acute hepatitis A, B, or C infection and liver imaging (eg, biliary tract) may be warranted. All cases confirmed on repeat testing as meeting the laboratory criteria defined above, with no other cause for LFT abnormalities identified at the time, should be considered potential Hy's law cases irrespective of availability of all the results of the investigations performed to determine etiology of the abnormal LFTs. Such potential Hy's law cases should be reported as SAEs.

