### 3.2. DLT Definition

Severity of AEs will be graded according to CTCAE version 4.03. For the purpose of dose escalation, any of the following adverse events occurring in the first cycle of treatment (28 days) will be classified as DLTs, unless there is a clear alternative explanation (eg, related to underlying disease/progression, change in concurrent medication or co-morbid event):

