**Non-hematologic:**

- Any toxicity attributable to PF-06840003 that results in administration of less than 80% of the planned doses during Cycle 1.
- Grade 4 non hematologic AE.
- Grade 3 AE lasting >7 days despite optimal supportive care.
- Grade 3 CNS AE regardless of duration. CNS AEs are those events listed within the nervous system disorders category in the NCI CTCAE version 4.03.
- Grade 3 QTc prolongation (QTc >500 msec) will be considered a DLT only if persisting after correction of any reversible causes.
- Concurrent aspartate aminotransferase (AST) or alanine aminotransferase (ALT) >3 x upper limit of normal (ULN) and total bilirubin >2 x ULN.

The following AEs will not be considered as DLTs:

- Isolated Grade 3 or 4 laboratory abnormalities that are not associated with clinical sequelae or are corrected to Grade  $\leq$ 1 with supplementation/appropriate management within 72 hours of their onset.

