  - d. Prothrombin time (PT) or partial thromboplastin time (PTT)  $< 1.5$  x upper limit of normal (ULN).
12. Adequate Renal Function, including:
  - a. Estimated creatinine clearance  $\geq 60$  mL/min as calculated using the Cockcroft-Gault calculator. A 24-hour urine collection is not required but should be used to confirm estimated creatinine clearance if a urine collection is obtained as part of standard of care.
13. Adequate Liver Function, including:
  - a. Total serum bilirubin  $\leq 1.0$  x ULN unless the patient has documented Gilbert syndrome or extrahepatic source by increased indirect bilirubin function;
  - b. Aspartate and Alanine transaminase (AST and ALT)  $\leq 1.5$  x ULN ( $\leq 3$  x ULN for patients on chronic anticonvulsive therapies known to increase transaminases)
  - c. Alkaline phosphatase  $\leq 1.5$  x ULN; ( $\leq 3$  x ULN for patients on chronic anticonvulsive therapies known to increase transaminases)
14. Serum or urine pregnancy test (for females of childbearing potential) negative at screening.
15. Male patients able to father children and female patients of childbearing potential and at risk for pregnancy must agree to use two highly effective methods of contraception throughout the study and for at least 28 days after the last dose of assigned treatment.

Female patients who are not of childbearing potential (ie, meet at least one of the following criteria):

- Have undergone a documented hysterectomy and/or bilateral oophorectomy;
  - Have medically confirmed ovarian failure; or
  - Achieved postmenopausal status, defined as follows: cessation of regular menses for at least 12 consecutive months with no alternative pathological or physiological cause and have a serum follicle-stimulating hormone (FSH) level within the laboratory's reference range for postmenopausal women.
16. Evidence of a personally signed and dated informed consent document indicating that the patient has been informed of all pertinent aspects of the study.
17. Patients who are willing and able to comply with scheduled visits, treatment plans, laboratory tests and other procedures.

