##### **5.4.1. Recommended Dose Modifications**

Every effort should be made to administer investigational product on the planned dose and schedule.

In the event of significant toxicity, dosing may be delayed and/or reduced as described below. In the event of multiple toxicities, dose modification should be based on the worst toxicity observed. Patients are to be instructed to notify investigators at the first occurrence of any adverse symptom.

Dose modifications may occur in one of three ways:

- Within a cycle: dosing interruption until adequate recovery and dose reduction, if required, during a given treatment cycle;
- Between cycles: next cycle administration may be delayed due to persisting toxicity when a new cycle is due to start;
- In the next cycle: dose reduction may be required in the current and/or subsequent cycle based on toxicity experienced in the current/previous cycle.

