#### **5.4.2. Dosing Interruptions**

Patients experiencing the following adverse events should have their treatment interrupted:

- Grade 3 or 4 potentially treatment related toxicity;
- Intolerable Grade 2 toxicity despite supportive care.

Appropriate follow up assessments should be done until adequate recovery occurs as assessed by the investigator. Criteria required before treatment can resume are described in [Section 5.4.3 Dose Delays](#).

Doses may be held as needed until toxicity resolution. Depending on when the AE resolved, a treatment interruption may lead to the patient missing all subsequent planned doses within that same cycle or even to delay the initiation of the subsequent cycle.

If the AE that led to the treatment interruption recovers within the same cycle, then re-dosing in that cycle is allowed. Doses omitted for toxicity are not replaced within the same cycle. The need for a dose reduction at the time of treatment resumption should be based on the criteria defined in section [Dose Reductions](#), unless expressly agreed otherwise following discussion between the investigator and the sponsor.

In the event of a treatment interruption for reasons other than treatment-related toxicity (eg, elective surgery) lasting >4 weeks, treatment resumption will be decided in consultation with the sponsor.

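### No explicit instruction to hold or stop PF-06840003 is tied to a potential Hy's law case; where each liver test is only Grade 2, the written default is to keep dosing

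*Protocol*

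**What the plan says.** **Liver criteria.** For a patient with normal baseline values, Protocol 8.6.2 flags AST or ALT of at least 3 x ULN together with bilirubin of at least 2 x ULN, provided there is no hemolysis and alkaline phosphatase is at most 2 x ULN or missing. Such events "should always be considered important medical events". A separate threshold applies "For patients with preexisting AST or ALT baseline values above the normal range", and another where baseline bilirubin is raised. The required actions are clinical and administrative: "The patient should return to the investigational site and be evaluated as soon as possible, preferably within 48 hours" of awareness, then repeat tests, a search for causes, and an SAE report if the case is confirmed with no other cause found.

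**DLT criterion.** Under Protocol 3.2, "any of the following adverse events occurring in the first cycle of treatment (28 days) will be classified as DLTs" unless another explanation is clear. The list includes "Concurrent aspartate aminotransferase (AST) or alanine aminotransferase (ALT) >3 x upper limit of normal (ULN) and total bilirubin >2 x ULN".

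**Dosing rules.** Protocol 5.4.1 states: "In the event of multiple toxicities, dose modification should be based on the worst toxicity observed". Section 5.4.2 calls for interruption for "Grade 3 or 4 potentially treatment related toxicity" and for Grade 2 toxicity that is intolerable despite supportive care; it also permits doses to be held as needed. Table 3 leaves the dose unchanged for non-hematologic Grade 2. Section 5.4.4 recommends no particular adjustment at Grade 1 or 2, then defers to medical judgment. It lets a patient with a DLT restart one level down after recovery, and it sends dose reductions for late or Part 2 toxicity to sponsor consultation. Section 5.4.3 bars both restart and the start of a new cycle until non-hematologic toxicity is at baseline or Grade 1, with Grade 2 accepted only if the investigator sees no safety risk.

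**The concern.** The liver criteria combine two tests, but the dosing rules look at one toxicity at a time. Two results that are each moderate can together meet the protocol's own definition of a potential Hy's law case and still count as Grade 2. In that situation the protocol has more than a gap: the row of Table 3 that applies says to carry on. Two sites could both follow the protocol, one holding the drug and the other dosing while the cause is unknown.

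The liver matters for this compound. Protocol 1.5.2 names it a target organ in the 1-month dog study, with minimal to mild hepatocellular degeneration, enzymes up to 19 times baseline and/or bilirubin 2 to 4 times baseline, largely reversible. The protocol does write event-specific hold rules elsewhere: for cerebral edema in 5.7.3 and for QTcF prolongation in 7.1.5. Potential liver injury has no counterpart.

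**Working it through.** The plan gives no figure to reproduce. The check has four steps.

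**1. Is there a Grade 2 plus Grade 2 band?** The protocol names CTCAE v4.03 but prints no liver cut-offs. Assumption: Grade 2 is AST/ALT above 3 to 5 x ULN and bilirubin above 1.5 to 3 x ULN. With normal baseline values, band width = Grade 2 ceiling minus 8.6.2 threshold:

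| Test | 8.6.2 threshold (x ULN) | Ceiling tried (x ULN) | Width (x ULN) |
|---|---|---|---|
| AST/ALT | 3 | 3, 4, 5 | 0, 1, 2 |
| Bilirubin | 2 | 2, 2.5, 3 | 0, 0.5, 1 |

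Both widths must be positive for the gap to exist. It vanishes if either ceiling is at the low end of its range.

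**2. Who is in the band?** Section 8.6.2 adjusts for baseline, with B and b as multiples of ULN.

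- AST/ALT: threshold = min(max(3, 2B), 8). Inclusion 13 admits up to 1.5 x ULN, or up to 3 x ULN "for patients on chronic anticonvulsive therapies known to increase transaminases".
- Bilirubin: threshold = 2 if b ≤ 1, otherwise min(b + 1, 3). Inclusion 13a admits b above 1 only with Gilbert syndrome or an extrahepatic source, and sets no upper limit for them.

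| Baseline (x ULN) | Threshold (x ULN) | Width under ceilings 5 and 3 |
|---|---|---|
| AST/ALT up to 1.5 | 3 | 2 |
| AST/ALT 2.0 | 4 | 1 |
| AST/ALT 2.25 | 4.5 | 0.5 |
| AST/ALT 2.5 | 5 | 0 |
| AST/ALT 3.0 | 6 | none |
| Bilirubin up to 1.0 | 2 | 1 |
| Bilirubin 1.5 | 2.5 | 0.5 |
| Bilirubin 2.0 | 3 | 0 |

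The band is therefore full for patients with AST/ALT up to 1.5 x ULN and normal bilirubin. It narrows above either limit, closing for AST/ALT above 2.5 x ULN (those cases would be Grade 3 and interrupted under 5.4.2) and at bilirubin 2.0 x ULN. The 3.2 criterion has no baseline adjustment.

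**3. Which dosing rule applies inside the band?**

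- *Part 1, Cycle 1.* An event meeting 3.2 with no clear alternative explanation is a DLT. The 5.4.4 sentence presupposes a stop and a lower dose; Table 3's Grade 2 entry says the opposite. No precedence is stated. At 125 mg no reduction is allowed, so the restart dose is undefined.
- *Later cycles and Part 2, mid-cycle.* 5.4.2 is not triggered unless the Grade 2 event is judged intolerable. A hold rests on the permissive wording in 5.4.2, medical judgment in 5.4.4, and the sponsor meeting in 3.4, which orders no interim hold for the affected patient.
- *Start of each new cycle.* 5.4.3 does bar dosing, unless Grade 2 is judged not to be a safety risk. From Cycle 2, chemistry is scheduled on Days 1 and 15, so a Day 15 finding comes 14 days before the next gate (29 - 15).

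**4. Exposure over the 48-hour recall period.** At 125 mg QD: 2 x 125 = 250 mg. Under the 1000 mg per day cap in 3.1: 2 x 1000 = 2,000 mg. At the 1000 mg BID level in Table 1: 4 x 1000 = 4,000 mg.

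**The case against.** The sponsor can fairly say that the protocol has several safety nets. A Cycle 1 event meeting 3.2 is a DLT and 5.4.4 speaks to it. Section 5.4.3 stops a new cycle from starting in most such patients. Medical judgment and as-needed holds are always available, late and Part 2 events meeting the DLT grading criteria trigger an immediate meeting, and confirmed cases reach the sponsor within 24 hours as SAEs. Table 3 is also headed as covering product-related toxicity, while during the work-up the cause is still open.

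Most of this stands, and it limits the point. A reader might infer that no dosing text at all attaches to the 3.2 criterion, or that the protocol obliges sites to dose through suspected liver injury. The documents support neither: the DLT sentence does attach to 3.2 in Cycle 1, and nothing forbids a hold. Nor is the gap the same for every patient, as the baseline adjustments show.

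What remains is that none of these routes requires a mid-cycle hold. Setting Table 3 aside because causality is unsettled does not supply one: 5.4.2, which covers potentially related events, still starts at Grade 3 or intolerable Grade 2, and two abnormal laboratory values without symptoms do not readily fit the latter.

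**Conclusion.** The concern holds in limited form. No explicit hold or discontinuation instruction is tied to a potential Hy's law case. Where both tests are only Grade 2, the grade-based default during the work-up is to continue unchanged. In Part 1 Cycle 1 that default conflicts with the 5.4.4 DLT sentence. After Cycle 1 and in Part 2 the weakness is confined to mid-cycle events, because 5.4.3 covers the start of each cycle.

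The conclusion rests on the assumed Grade 2 ceilings of 5 x and 3 x ULN, on the ranges shown, and on the visible text; some protocol passages are redacted and could not be checked. No incidence is claimed, and such events may be rare. The correction is worth making because it concerns the safety of individual patients in a first-in-patient study and costs little.

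**What to change.** Add to Protocol 5.4.2 and Table 3, overriding the Grade 2 entry:

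> Interrupt PF-06840003 for any event meeting the baseline-adjusted criteria of 8.6.2 (or the 3.2 liver DLT criterion in Part 1 Cycle 1), whatever the grade of each test, pending repeat testing and work-up. If the event is not confirmed or another cause is identified, resume under 5.4.3. If it is confirmed with no other cause, resume only after AST, ALT and bilirubin return to Grade ≤1 or baseline and with sponsor agreement on dose reduction (within 5.4.4), or discontinue permanently.

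Cross-refer from 3.2 and 8.6.2. Using the baseline-adjusted criteria outside Part 1 Cycle 1 avoids holding a patient with Gilbert syndrome for a transaminase rise alone. Sending unconfirmed or otherwise explained events back to 5.4.3 keeps the investigator's existing discretion.

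The cost is a short insertion and two cross-references in the next amendment, plus a few missed doses in rare patients whose event proves unconfirmed. In Part 1 Cycle 1, a hold not due to attributable toxicity could make a patient non-evaluable for the MTD under 9.1 and require replacement. That happens below 50% of planned dose: 15 or more of 28 QD doses missed (13/28 = 46.4%) or 29 or more of 56 BID doses missed (27/56 = 48.2%). A brief hold for repeat testing stays well short of that.
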